5.3.3.1. Phase Allocation of Adverse Events

Solicited events are always allocated to the respective Post Dose period.

Step 1: Allocation of events to the periods:

Adverse events in the SDTM data base are allocated to periods based on their start date/time. If the start date/time of an event falls between (or on) the start and stop date/time of a period, the AE is attributed to that period (treatment-emergent principle).

- In case of partial start or stop dates (i.e. time and/or day and/or month and/or year missing), the events are allocated to the periods using the available partial information on start and end date; no imputation will be done. If, for instance, the AE start date only month and year are available, these data are compared to the month and year information of the periods. This rule may lead to multiplication of the event as a consequence of its assignment to multiple periods.
- In case of a completely missing end date, the date is imputed by the cut-off date of the analysis for participants still ongoing in the study, and by the end date of the last period for participants who discontinued or completed the trial. In case of a completely missing start date, the event is allocated to the first active treatment phase (post dose 1 period), except if the end date of the AE falls before the start of the first active treatment phase (post dose 1 period).

Step 2: Combination of events:

Overlapping/consecutive events are defined as events of the same participant with the same preferred term which have at least 1 day overlap or for which the start date of an event is 1 day after the end date of the preceding event. Overlapping/consecutive events may be combined into one AE or not, according to the following rules:

1. If overlapping/consecutive events start in one of the following periods - Screening or post dose extension (i.e. non-active periods) - followed by an AE in - post-dose period (active period) - they are allocated to their respective periods and are considered as separate events.
2. In case overlapping/consecutive events start within a single period, they are considered as one and the same AE. The individual events which contribute to this AE are retained as individual records in the ADaM data base but are assigned the same onset, period, and total duration. All related attributes to the AE/phase/period should also be consistent with the new event.
3. In case overlapping/consecutive events start in both an active period followed by a non-active period, they are allocated to the active period only and are considered as one and the same AE. The individual events which contribute to this AE are retained as individual records in the ADaM data base but are assigned the same onset, treatment period, and total duration. All related attributes to the AE/phase/period should also be consistent with the new event.

4. In case an active period is followed by another active period, and the overlapping/consecutive events start in both periods, they are allocated to their respective period and are considered as separate AEs. The same rule applies for 2 non-active periods.

Remarks:

1. Events can only be combined into one and the same AE if their start and stop dates are known.
2. In case the completely missing end date is imputed (for period allocation), this date is also considered as a complete date.
3. Time is not considered when determining overlap of events.

5.3.3.2. Missing Data

Missing data will not be imputed. Participants who do not report an event/concomitant medication will be considered as participants without an event/concomitant medication. An AE with a missing severity or relationship will be considered as an AE reported but will be considered as not reported for the severity or relationship. For example, an AE with missing severity will be considered as an AE reported for the analysis of any grade but will be considered as not reported for the analysis of at least grade 3.

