8. STUDY ASSESSMENTS AND PROCEDURES

Overview

The Schedule of Activities (Section 1.4) summarizes the frequency and timing of safety, reactogenicity, immunogenicity, and other measurements applicable to this study. All participants in the study will be counselled on COVID-19 prevention each time that they have a contact with study site staff in line with local guidelines.

If multiple assessments are scheduled for the same timepoint, it is recommended that procedures be performed in the following sequence: vital signs before blood draws. If needed, assessments may be performed at another day within the applicable visit window. Actual dates and times of assessments will be recorded in the source document and in the eCRF.

Participants will be provided a thermometer (to measure body temperature), ruler (to measure local injection site reactions), and participant diary to record body temperature and solicited local (at injection site) and systemic signs and symptoms. The diary includes instructions on how to capture the data and grading scales to assess severity of the signs and symptoms post vaccination (reactogenicity). The study staff is responsible for providing appropriate training to the participant

to avoid missing or incorrect data. The diary will be reviewed by the study personnel at visits indicated in Section 1.4, Schedule of Activities. If the diary review is missed, the diary will be reviewed during the following visit. If a participant misses a vaccination, the diary covering the period after the missed vaccination does not have to be completed.

The total blood volume to be collected from each participant over the course of the main study will be approximately 119 mL. The total blood volume to be collected from each participant over the course of the sub study will be approximately 163 mL. Repeat or unscheduled samples may be taken for safety reasons or for technical issues with the samples. For participants who experience a suspected AESI, an additional 30 mL of blood will be collected.

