9.4.3. Secondary Endpoint(s)

Immunogenicity Endpoints

Descriptive statistics (geometric mean and confidence intervals, or median and interquartile range Q1-Q3, as appropriate) will be calculated for continuous immunologic parameters. Several definitions of serological response will be applied as applicable (GMC [S-ELISA]). Graphical representations of immunologic parameters will be made as applicable. Frequency tabulations will be calculated for discrete (qualitative) immunologic parameters, as applicable.

In addition, the ratio between neutralizing and binding antibodies as determined by S-ELISA and VNA, respectively, will be calculated together with confidence intervals. More details will be provided in the SAP.

The immunogenicity analyses will be performed on the PPI population. Immunogenicity analyses will also be done on the FAS (participants who became infected during the study will be analyzed as a subgroup and shown in the graphs using different colors and symbols).

Safety Endpoints

No formal statistical testing of safety data is planned. Safety data will be analyzed descriptively by vaccine group. In addition, for selected tables, tabulations pooled by vaccine dose will also be provided. All safety analyses will be made on the FAS.

Adverse Events

The verbatim terms used in the eCRF by investigators to identify AEs will be coded using the Medical Dictionary for Regulatory Activities (MedDRA). All reported AEs with onset during the active vaccination phase (ie, AEs occurring after vaccination up to 28 days post vaccination), and all SAEs/MAAEs/AESIs will be included in the analysis. (S)AEs caused by molecularly confirmed SARS-CoV-2 infection will be removed at the analysis level from the (S)AE listings and tables and presented separately. For each AE, the percentage of participants who experience at least 1 occurrence of the given event will be summarized by vaccine group.

Summaries, listings, datasets, or participant narratives may be provided, as appropriate, for those participants who die, who discontinue intervention due to an AE, or who experience a severe AE, an AESI, or an SAE.

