4. POPULATIONS (ANALYSIS SETS) FOR ANALYSIS

For vaccine studies, study intervention assignment will follow the as treated principle: all analyses (including safety, immunogenicity) will be analyzed by the received vaccine.

Analysis Sets	Description
All screened participants (ALL)	The “all screened participants” set includes all participants that were screened, regardless of whether they were enrolled and/or randomized.
All randomized participants (ALL RANDOMIZED)	The “all randomized participants” set includes all participants that were randomized to one of the treatment groups.
Full Analyses Set (FAS)	The Full Analysis Set will include all participants with at least one vaccine administration documented
Per Protocol Immunogenicity Set (PPI)	The Per Protocol Immunogenicity population will include all randomized and vaccinated participants for whom immunogenicity data are available excluding participants with major protocol deviations expected to impact the immunogenicity outcomes (see section 4.1). In addition, samples obtained after missed vaccinations or samples obtained from participants after SARS-CoV-2 infection occurring after screening (if applicable) will be excluded from the analysis set (see below section 4.1).
NI Analysis Set	The NI analysis set will include all PPI participants who are SARS-CoV-2 seronegative at study entry ^a .

^a SARS-CoV-2 seronegative as assessed by central testing (based on S- and/or N- serology at baseline)

NB. As detailed in Section 4, formal non-inferiority hypothesis testing will be performed on either the NI set or on the PPI set under different scenarios (Scenario 1 or Scenario 2, respectively).

Further details on the selection of PPI and NI set are described below.

The safety and reactogenicity analyses will be censored at the date of unblinding or the receipt of an unscheduled vaccine, whichever event occurs first. AEs reported after unblinding or receipt of an unscheduled vaccine, whichever comes first, will be listed.

The immunogenicity analyses will be censored at the date of the receipt of an unscheduled vaccine. Immunogenicity samples taken after the receipt of an unscheduled vaccine will be included in the listings and flagged.

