5. STATISTICAL ANALYSES

5.1. General Considerations

5.1.1. Study Phases

A baseline (or reference) value will be defined as the value of the last available assessment prior to the first vaccination on Day 1, unless specified otherwise. The safety analysis will present all results by phase (see Section 5.2).

Immunogenicity results will be presented per scheduled time point as appropriate using visit windows (see section 1.4 in the protocol). Listings will be presented per phase and time point.

Study day or relative day is defined as follows:

Study Day = visit date - date of Day 1 + 1; if visit date \geq date of Day 1 (date of first vaccination).

Study Day = visit date - date of Day 1; if visit date $<$ date of Day 1 (date of first vaccination).

Relative day (relday), the number of days in the analysis time point will be defined as:

relday = visit date - reference date + 1 for visits on or after the reference date,

relday = visit date - reference date for visits before the reference,

where the reference date equals the date of vaccination 1 or 2.

The planned primary and final analysis will be performed on unblinded data. During primary analysis data will be unblinded to the sponsor.

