5.3. SAFETY

No formal statistical testing of safety data is planned. Safety data will be analyzed descriptively by vaccine group. In addition, for selected tables, tabulations pooled by vaccine dose will also be provided. All safety analyses will be done on the FAS. This will be done for both the main study and sub study separately.

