5.3.3. Analysis of Adverse Events

The number and percentage of participants with at least one AE (unsolicited/solicited) will be tabulated. Unsolicited AEs will be summarized by System Organ Class and Preferred Term. Solicited AEs will be summarized by class (administration site, systemic) and preferred term.

For solicited AEs, the following tables will be provided: summary, by worst severity grade, at least grade 3, related (systemic only), time to onset (in days) and duration (in days) for most frequent events (>1%) and body temperature. Note: Duration is defined as number of days from the start of the event until resolution of the event. The time to first onset is defined as (date of first onset – reference date + 1). The reference date is the start date of the first vaccination period.

For unsolicited AEs, the following tables will be provided: summary table (including SAE, MAAEs, MAAEs leading to study discontinuation, fatal outcome, and discontinuation), all events, most frequent (>1%), at least grade 3, related and SAE. The proportion of AEs resulting in a medically attended visit (other than routine health maintenance visits) will also be tabulated.

For AESI, the following summary tables will be provided on suspected and qualified for assessment of AEs of Special Interest (AESI) by vaccine group:

1. Number of Suspected AE of Special Interest (AESI) (as Reported by Investigator) by SMQ and Preferred Term.

Note: Suspected AESI as reported by investigator and presented by: Embolic and thrombotic events (SMQ); Haematopoietic thrombocytopenias (SMQ) (broad) or HLT Thrombocytopenias; Other SMQ.

2. Number of Suspected AE of Special Interest (AESI) (Identified through SMQ search) by SMQ and Preferred Term.

Note: Suspected AESI Identified through SMQ search: Embolic and thrombotic events (SMQ), Haematopoietic thrombocytopenias (SMQ) (broad) or HLT Thrombocytopenias and presented by: Embolic and thrombotic events (SMQ) + sub-SMQ1 + PT; Haematopoietic thrombocytopenias (SMQ) (broad) or HLT Thrombocytopenias + PT;

3. Number of AESI Qualified for assessment by SMQ and Preferred Term.

Note: AESI Qualified for assessment: [Embolic and thrombotic events (SMQ)] and [Haematopoietic thrombocytopenias (SMQ) (broad) or HLT Thrombocytopenias or platelet count below normal ranges per local or central laboratory report or platelet count < 150 × 10E9/L]

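### Solicited reaction rates count dosed participants with no reactogenicity data as having had no reaction

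*SAP*

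**What the plan says.** SAP 5.3.3.2 (Missing Data) first says "Missing data will not be imputed" and then that "Participants who do not report an event/concomitant medication will be considered as participants without an event/concomitant medication". No distinction is made between solicited and unsolicited events.

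The analysis set is the same throughout. SAP 5.3 says "All safety analyses will be done on the FAS", and Protocol 9.4.3 says "All safety analyses will be made on the FAS". SAP section 4 defines the set: "The Full Analysis Set will include all participants with at least one vaccine administration documented". It lists no reactogenicity or diary-data set.

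For the tables, SAP 5.3.3 says "The number and percentage of participants with at least one AE (unsolicited/solicited) will be tabulated" and gives no denominator. SAP 5.3.2.1 takes the tabulated solicited events from the investigator assessment (CE) pages of the case report form. Protocol 8.3.2 describes how those pages are filled: participants record signs and symptoms in a diary, and the investigator reviews and discusses the entries before completing an assessment.

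**The concern.** Treating no report as no event is the usual convention for unsolicited events, where the absence of a report is the only evidence there can be. Solicited events are different. The participant is asked about a fixed list every day, so a completed diary with no reaction is a real negative, and an empty record is not. The SAP rule merges the two. Although the section opens by ruling out imputation, for solicited events the rule in effect imputes a negative for everyone without data.

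Solicited local and systemic events after each vaccination are a secondary endpoint in both the main study and the sub study. Safety is descriptive with no formal testing, so the tabulated percentages are themselves the result. They are also the figures a reader would use to compare reactogenicity across dose levels, including 9x10^10 vp, which the protocol evaluates as the upper limit of the release range.

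**Working it through.** The plan states no expected reactogenicity rate for this trial and no rate of missing reactogenicity data, so there is no figure to reproduce. The check is a reading of the rules followed by dilution arithmetic on stated assumptions.

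**Reading the rules together**

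1. A participant with one documented dose is in the full analysis set (SAP 4), and all safety analyses use that set (SAP 5.3, Protocol 9.4.3).
2. If that participant has no solicited record after the dose, SAP 5.3.3.2 classes them as without the event.
3. They therefore add one to the denominator and cannot add to the numerator.

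**Formula**

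Reported rate = p x (1 - m), so the shortfall is p x m. Here p is the true rate and m is the share of the denominator with no solicited data. This assumes reactions are equally frequent in those with and without data.

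**Inputs**

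- p = 64%: solicited systemic events in Cohort 1 (ages 18 to 55) of the first-in-human study, Protocol 2.3.1. This comes from blinded data in another study and is illustrative only. p = 60% is a rounder assumption alongside it.
- m = 2%, 5% and 10%: assumptions, because the documents give nothing.

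**Results**

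| m | p = 60% | shortfall (points) | p = 64% | shortfall (points) |
|---|---|---|---|---|
| 2% | 60 x 0.98 = 58.8% | 1.2 | 64 x 0.98 = 62.7% | 1.3 |
| 5% | 60 x 0.95 = 57.0% | 3.0 | 64 x 0.95 = 60.8% | 3.2 |
| 10% | 60 x 0.90 = 54.0% | 6.0 | 64 x 0.90 = 57.6% | 6.4 |

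In a group of 225, m of 2 to 10% is 225 x 0.02 = 4.5 to 225 x 0.10 = 22.5 participants.

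**Between-group comparison**

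With equal m in two groups, the ratio of reported rates is p1(1 - m) / p2(1 - m) = p1 / p2. The ratio is unchanged, and the absolute difference shrinks by the factor (1 - m). With unequal m, say 2% against 10% and the same true 64%, the table would show 62.7% against 57.6%. That is a gap of 64 x 0.08 = 5.1 points with no real difference.

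**Post-dose 2 tables**

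- SAP 5.1.1 presents safety results by phase. SAP 5.1.2 starts the post-dose 2 period at the second vaccination, so a participant without dose 2 has no such period.
- SAP 5.2 tabulates participants per phase, and SAP 5.2.2 counts recipients at Day 1 and Day 57.
- None of these sections names its count as the denominator of the adverse event tables. Table mock-ups are left to the Data Presentation Specifications (SAP 1), which are not among the documents.

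**The case against.** The strongest reply is that missing solicited data should be uncommon. The tables draw on the investigator's pages and not on the raw diary. In the main study the site telephones participants 7 days after each vaccination about diary completion (Protocol 1.4.1, note c). A missed diary review is made up at the following visit (Protocol 8), and staff document solicited events after the 15-minute observation. This stands, and it limits the point. A reader might infer that every participant without a diary is counted as reaction-free, but a missing diary is not by itself missing data. The dilution needs a dosed participant with no investigator assessment either.

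A second temptation is to say that participants who never received dose 2 pull down the post-dose 2 rates, so that missing people could produce an apparent fall in reactogenicity from dose 1 to dose 2. Protocol 8 makes this look plausible, since "the diary covering the period after the missed vaccination does not have to be completed". The documents do not support it as a finding. No section puts one-dose participants in the post-dose 2 denominator, and the phase definitions point the other way. What remains is that the denominator is not stated.

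It can also be said that safety is descriptive, that the primary non-inferiority endpoint is untouched, and that randomisation with blinded participants makes similar missingness across groups likely. All of this is fair, and no document shows unequal missingness. It reduces the risk to the comparison but leaves the downward bias in each rate.

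**Conclusion.** The concern holds for solicited events in participants who received the dose and have no solicited data after it. For them the SAP is not merely silent. It states a rule that, followed as written, biases the reported rates downward. The relative bias equals the share without data. With an assumed true rate of 60 to 64% and an assumed 2 to 10% without data, it is about 1 to 6 percentage points. The actual size cannot be determined from the documents, and it would be smaller if people without data reacted less often than the rest. Comparisons between dose groups are distorted only if missingness differs between them, which is possible but not shown.

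The post-dose 2 denominator is a separate and lesser matter: the SAP should state it, and the likely intention is dose 2 recipients. The rule is acceptable for unsolicited events.

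**What to change.** In SAP 5.3.3.2, limit the no-report-means-no-event rule to unsolicited events, serious events and concomitant medication. In SAP 5.3 or 5.3.3, add that:

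- each post-dose solicited event table uses full analysis set participants who received that dose and have at least one diary entry or investigator solicited assessment after it;
- the number of dosed participants without such data is shown by dose group, so that a reader can bound the effect of leaving them out;
- post-dose 2 adverse event tables use participants who received dose 2.

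This needs no new data collection. The cost is SAP wording, one denominator flag, and reported solicited rates that will be slightly less favourable.

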5.3.4. Laboratory, Vital Signs and Physical Examination

Laboratory safety parameters, change from baseline and change from pre-dose over time will be tabulated. Abnormalities on the changes from reference, if available, may be categorized. Abnormalities may be tabulated by visit and by worst abnormality. Patient profiles may be provided.

A listing of all laboratory values will be made, restricted to participants with at least one laboratory abnormality.

Hematology laboratory parameters before and after Ad26.COV2.S administration.

Including but not limited to: Lupus anticoagulants, anti- β 2 glycoprotein, anti-cardiolipin, D-dimers, platelet count and anti-PF4

Physical examination findings will be summarized at baseline. A listing of the abnormalities will be made.

Vital signs including temperature, pulse/heart rate, respiratory rate, and blood pressure (systolic and diastolic) will be summarized over time, using descriptive statistics. Abnormalities emerging after vaccination will be tabulated by worst abnormality grade using the FDA table in [Appendix 2](#).

An abnormality (toxicity grade or abnormality based on normal ranges) will be considered as emerging in a particular period if it is worse than the baseline value. If the baseline is missing, the abnormality is always considered emerging. A shift from 'abnormally low' at baseline to 'abnormally high' post baseline (or vice versa) is also emerging. In case a laboratory test result is censored (no numeric value is available, but only a verbatim term) then a numeric value will be

imputed by a value exceeding the cut-off value with one unit. (<x: subtract 1 unit from x, >x: add 1 unit to x; <3.45 is imputed with 3.44).

In case no toxicity grades are defined for a test, the abnormalities (above/below normal range) will be used. In determining toxicity grades, the following rules are applied:

-worst grades/abnormalities are determined over the whole observational period for each trial period separately, including all post-baseline measurements of that period.

- The abnormalities 'abnormally low' and 'abnormally high' are considered equally important, i.e. if a participant has as well an abnormally low as an abnormally high value post-baseline, both abnormalities are shown in the tables. (This means that the sum of the percentages can be more than 100%)

- Note: as the grading scale for some parameters in the grading table has some gaps (zones where no toxicity grade definition exists), laboratory results falling in these zones will be allocated to the adjacent worst-case grade.

- If a lab value falls within the grading as specified in the grading table but also within the local lab normal limits, the value is considered as normal.

For the grades, no distinction will be made between test results of samples obtained under fasting and under non-fasting conditions: in case limits under fasting and non-fasting conditions differ, the limits of the conditions (fasting/non-fasting) of scheduled visits as planned in the CTP will always be used, also for samples obtained under a different condition (e.g. samples of withdrawal visits).

A listing of participants with fever according to the FDA grading table will also be provided. In addition, temperature measurements (whether obtained from the diary or from on-site assessments) will be allocated to predefined temperature intervals (from 37.5° C until 40°C, in steps of half degree increments, e.g. <37.5, 37.5-<38, 38-<38.5, ... >40), and tabulated.

